# **GLOSSARY OF ABBREVIATIONS**

AE	Adverse Event
CI	Chief Investigator
CRF	Case Report Form
DMC	Data Monitoring Committee
DOB	Date of Birth
GCP	Good Clinical Practice
HRA	Health Research Authority
ICF	Informed Consent Form
ID	Identification number
ISF	Investigator Site File
NHANES	National Health and Nutrition
	Examination Survey
PI	Principal Investigator
PIS	Participant Information Sheet
RB&HFT	Royal Brompton and Harefield NHS
	Foundation
REC	Research Ethics Committee
SAE	Serious Adverse Event
SOP	Standard Operating Procedure
SP	Subject Patient
VAS	Visual Analogue Scale

# **KEYWORDS**

[Nebulised Hypertonic Saline, Neuromuscular disease, Cerebral Palsy, Children, Respiratory complications, Polygraphy]

# STUDY SUMMARY

TITLE A Chart Review assesing the effects of Nebulised Hypertonic Saline on Respiratory-related complications in children and young people with Neuromuscular Disease or Cerebral Palsy

**DESIGN** Chart Review and Questionnaire application

AIMS 1)To explore whether treatment with 7% or 3% nebulised Hypertonic Saline in children and young people with Neuromuscular Disease or Cerebral Palsy decreases respiratory-related complications.

2) Assess whether the use of 3% or 7% nebulised Hypertonic Saline improves ease of airway clearance in children and young people with Neuromuscular Disease or Cerebral Palsy

#### **OUTCOME MEASURES**

- 1) Number of respiratory exacerbations requiring antibiotic treatment.
- 2) Number of hospitalisations due to respiratory exacerbations, using NHANES 2011 questionnaire for Hospitalisation and access to care HUQ.010.
- 3) Nocturnal oximetry and polygraphy outcomes: BasalSpO2 (%), Minimum SpO2 (%), Maximum SpO2 (%), Average SpO2, Oxygen desaturation index (ODI), Snoring and End tidal CO2 (EtCO2).
- 4) Rate of decline of pulmonary function.
- 5) Score on the ease of airway clearance pictorial analogue scale from participants.
- 6) Participants' perception of treatment.

## POPULATION

Children and young people with Neuromuscular disease or Cerebral Palsy who are treated at Royal Brompton Hospital and their parents or legal guardians.

#### **ELIGIBILITY**

Inclusion cirteria: Children and young people with Neuromuscular disease or Cerebral Palsy who have their care at the Royal Brompton Hospital and are on treatment with nebulised Hypertonic Saline for at least 12 months.

Exclusion criteria: Children or young people also diagnosed with Cystic Fibrosis.

**DURATION** 6 months

#### REFERENCE DIAGRAM

[if appropriate]

#### 1. INTRODUCTION

#### 1.1 BACKGROUND

In the UK, Neuromuscular diseases have a prevalence of 118 per 100,000 people amongst adults and children. About 70% are inherited, and 13% are muscular dystrophies (1). Worldwide, the prevalence of Cerebral Palsy is 2.11 per 1000 live births (2).

The pathophysiology of neuromuscular diseases and cerebral palsy leads to restrictive pathology of the respiratory system. Children with neuromuscular diseases have several characteristics that may impair their respiratory function, such as weak bulbar and respiratory musculature, increased upper airway collapsibility and low lung compliance (3,4). Cerebral Palsy is defined as a group of disorders of the motor function, caused by a disturbance to the developing brain (5). Although pulmonary disease is not the primary diagnosis, some clinical characteristics may lead to respiratory failure. These include scoliosis, gastroesophageal reflux, and impaired swallowing, which leads to chronic aspiration, upper airway obstruction, recurrent infections, and possible bronchiectasis, developing lung disease (6). Bulbar musculature weakness impairs swallowing, which leads to chronic aspiration. Respiratory muscle weakness compromises the pump function and the effectiveness of cough. Upper airway collapsibility increases work of breathing and respiratory muscle fatigue. Low pulmonary compliance hinders the ability to expand the lung, which is exacerbated by respiratory muscle weakness, increasing the WOB. Low peak flow and decreased Vital Capacity (VC), which further decreases with progression of the disease (7), characterizes the pulmonary function of these patients. Consequently, cough may be impaired by low inspiration volumes, ineffective glottis closure and/or low expiratory force (4.8,9). Low Vital Capacity and ineffective cough in Neuromuscular disease has been associated with chronic airway inflammation and infection (9). Furthermore, children with Neuromuscular disease often have gastroesophageal reflux (GER) (10), which may cause airway inflammation (11). Chronic airway infection and colonisation of Pseudomonas aeruginosa and Gram-negative microorganisms have shown to increase morbidity of children with CP (12). GER, impaired swallowing and ineffective cough leads to chronic aspiration and contributes to recurrent pneumonias. Therefore, bronchiectasis and pulmonary fibrosis are commonly developed.

Children with Neuromuscular disease show a decline of Forced Vital Capacity (FVC), which is steeper at younger ages (13). This is especially important because the age at which FVC reaches 1 Lt and the rate of decline of FVC are variables that can predict mortality (14).

Pneumonia, respiratory exacerbations and failure are one of the most important causes of emergency admissions, hospitalisations and death in children with neuromuscular diseases and cerebral palsy (15-18). Physical health and the number of days spent outside home or hospitalised are important domains of life and predictor of Health-Related Quality of Life in children with Neuromuscular disease and children with Cerebral Palsy (19,20). In this context, it is of importance to research how to therapeutically aid airway clearance, decrease respiratory exacerbations and reduce the pulmonary function rate of decline.

Hypertonic Saline is a solution of salt water used as a nebulized medication in many conditions. Its clinical benefits include mucus clearance, microbiological diagnosis, improvement of lung function, decrease in respiratory exacerbations, cough triggering and improvement of quality of life (21). It has mucolytic and expectorant effect, reduces biofilm formation by Pseudomonas Aeruginosa and increases antioxidative thiols in the airway liquid (22).

Retrospective studies and clinical trials have shown that inhaled Hypertonic Saline is well tolerated, reduces pulmonary exacerbations, improves lung function and Lung Clearance Index, reduces absenteeism, improves Health Related Quality of Life in patients with Cystic Fibrosis independent of rhDNase treatment (23-26), and has anti-inflammatory effect in sputum decreasing

IL-8 (27). In asthmatic and healthy subjects, inhaled Hypertonic Saline have shown to enhance mucociliary clearance (28). To date, studies investigating Hypertonic Saline in bronchiectasis have produced conflicting results (29).

This study aims to assess the effectiveness of the use of nebulised Hypertonic Saline in respiratory outcomes in children and young people with Neuromuscular disease or with Cerebral Palsy.

#### 1.2 RATIONALE FOR CURRENT STUDY

[To our knowledge, there is currently no available data concerning the use of nebulised Hypertonic Saline in the management of children and young people with Neuromuscular Disease or with Cerebral Palsy. This study aims to assess whether the use of nebulised Hypertonic Saline in children and young people with Neuromuscular disease or Cerebral Palsy is effective in the management and prevention of respiratory-related complications.

Hypothesis: Nebulised Hypertonic Saline in children and young people with Neuromuscular disease or Cerebral Palsy decreases respiratory-related complications.]

## 2. STUDY OBJECTIVES

[Primary Objective: To explore whether treatment with 3% and 7% Nebulised Hypertonic Saline in children and young people with Neuromuscular Disease or Cerebral Palsy decreases respiratory-related complications.

## Secondary Objectives:

- Assess the effect of the treatment with nebulised hypertonic saline in children and young people with Neuromuscular disease or Cerebral Palsy on the number of courses of antibiotic prescribed compared to year before starting treatment.
- Determine whether the use of nebulised Hypertonic Saline in children and young people with Neuromuscular Disease or Cerebral Palsy reduces the frequency of hospitalisations due to respiratory exacerbations compared to year before commencing treatment.
- Explore the impact of the treatment with hypertonic saline on nocturnal oxygenation and ventilation in children and young people with Neuromuscular disease or with Cerebral Palsy.
- Evaluate whether the treatment with nebulised hypertonic saline in children and young people with neuromuscular disease or cerebral palsy improves the ease of airway clearance.
- In the subgroup of participants with neuromuscular disease who can perform spirometry, assess whether the use of Hypertonic Saline decreases rate of decline of pulmonary function compared to year before commencing treatment.
- Explore how parents of children and young people with Neuromuscular disease or with Cerebral Palsy perceive the treatment with nebulised hypertonic saline compared to previous management.

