# 3. STUDY DESIGN

[Chart review of children and young people with Neuromuscular disease or with Cerebral Palsy who are cared for in the Royal Brompton Hospital and that have been treated with nebulised hypertonic saline for at least 12 months. Children and young people who are also diagnosed with Cystic Fibrosis will be excluded.

Parents or legal guardians will be asked to complete two questionnaires to further complement data from hospital records.

Participants between 10 and 18 years old will be asked to complete one questionnaire to complement hospital records.]

[Duration: 6 months.]

[We aim to review all charts of participants recruited that meet criteria between December 2011 and May 2018. We aim to recruit 40 participants from each group, including children, young people, and parents or legal guardians, as this will be a pilot study. Only participants recruited will have their charts reviewed]

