#### 3.1 STUDY OUTCOME MEASURES

**Primary Endpoints:** 

- Number of respiratory exacerbations requiring antibiotic treatment.
- Number of hospitalsiations due to respiratory exacerbations, using NHANES 2011 questionnaire for Hospitalisation and access to care HUQ.010.
- Nocturnal oximetry and polygraphy outcomes: Basal SpO2 (%), Minimum SpO2 (%), Maximum SpO2 (%), Average SpO2 (%), Oxygen desaturation index (ODI), Snoring and End tidal CO2 (EtCO2).
- Rate of decline of pulmonary function.

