# Statistical Analysis Plan:

Primary endpoint analysis:

- Univariate X analysis for categorical variables to investigate *Courses of antibiotic treatment*.
- Univariate X analysis for categorical variables to investigate *Number of hospitalisations*.
- Student t testing will be used to analyse *nocturnal oxygenation and ventilation outcomes* comparing one year before and after starting treatment with Hypertonic Saline.
- Independent t testing and Mann-Whitney U test to analyse *Rate of decline in pulmonary function*.
- Cox proportional hazard model to test differences in primary endpoints *for different baseline*

Secondary enpoint analysis:

- Univarate analysis to analyse *Ease of airway clearance*.
- Univariate analysis on **perception of treatment**.

Data and all appropriate documentation will be stored for a minimum of 10 years after the completion of the study, including the follow-up period.

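### The spirometry subgroup has no date for the ability that defines it and the planned tests are unpaired, so loss of spirometry after the start of saline can bias the lung-function comparison, possibly in favour of saline

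*Combined protocol and SAP*

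**What the plan says.** The lung-function objective in Section 2 (Secondary Objectives) reads: "In the subgroup of participants with neuromuscular disease who can perform spirometry, assess whether the use of Hypertonic Saline decreases rate of decline of pulmonary" (lung function is meant). The comparison is with the year before treatment. No date is attached to the ability. No minimum number of tests is set, and nothing is said about a child who loses the ability.

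Section 3.1 (Primary Endpoints) lists "Rate of decline of pulmonary function" with neither the neuromuscular nor the spirometry restriction. The same outcome is therefore a primary endpoint in one section and a secondary, restricted objective in another.

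Sections 3 and 4.2 require at least 12 months of saline before a child can enter. Section 3 adds: "We aim to review all charts of participants recruited that meet criteria between December 2011 and May 2018", and "Only participants recruited will have their charts reviewed".

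For this endpoint the Statistical Analysis Plan in Section 6 gives "Independent t testing and Mann-Whitney U test to analyse" the rate of decline. It has no paired test, slope model or missing-data rule.

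On disease course, Section 1.1 states: "Low peak flow and decreased Vital Capacity (VC), which further decreases with progression of the disease (7), characterizes the pulmonary function of these patients". It also says that the fall in forced vital capacity is steeper at younger ages.

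**The concern.** Every child is recruited at least a year after starting saline, so an undated ability is easily read as ability at recruitment or throughout follow-up. Either reading lets events after the start decide who is in the subgroup. A child who could be tested in the before-year and became too weak in the after-year may then supply no after-year slope. Because the tests are unpaired, that child's before-year slope can still stay in the comparison.

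If the children lost are those declining fastest, the remaining after-year slopes look better than the full set would. The apparent slowing would be in the direction of the study hypothesis, on an outcome that Section 3.1 calls primary.

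**Working it through.** **No figure to reproduce.** The plan gives no slope, SD, loss rate or subgroup size for spirometry. The target of 40 per group is justified only as a pilot. All inputs below are assumptions, used to find the direction and range of the bias when saline has no effect.

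**1. Loss through a steep after-start fall.** Let slopes be normal with equal mean and SD in both years and correlation ρ within child. The worst-declining fraction p of after-year slopes is lost.

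- Shift in the mean after-year slope of those remaining = φ(z_p)/(1−p): 0.195 SD at p = 0.10 and 0.350 SD at p = 0.20.
- *Unpaired*, all before-slopes against the remaining after-slopes: the full shift, about **0.20–0.35 SD**.
- *Same children in both years*: the before-year mean moves by ρ × shift, so the net bias is shift × (1−ρ):

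| Lost | ρ = 0.3 | ρ = 0.5 | ρ = 0.7 |
|---|---|---|---|
| 10% | 0.136 | 0.097 | 0.058 |
| 20% | 0.245 | 0.175 | 0.105 |

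That is about **0.06–0.25 SD**.

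**2. Loss through low level.** Suppose ability goes when vital capacity at the end of the after-year is low. End level = starting level + before-change + after-change. With equal variances, both changes have the same covariance with end level, so excluding low levels shifts both means equally. With the same children in both years the net bias is **0**.

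**3. Simulation check.** 2,000,000 children, no treatment effect, FVC 60% predicted (SD 15) one year before the start, mean change −5 points in each year. Slope SD is 3 between and 4 within child, so total SD = √(9+16) = 5 and ρ = 9/25 = 0.36. Entries are after-minus-before in points per year; positive favours saline.

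| Reason for loss | Lost | Same children | Unpaired |
|---|---|---|---|
| Low end level | 10% | 0.00 | +0.39 |
| Low end level | 20% | 0.00 | +0.70 |
| Steep after-start fall | 10% | +0.63 | +0.98 |
| Steep after-start fall | 20% | +1.12 | +1.75 |
| Unrelated to slope | 10% or 20% | 0.00 | 0.00 |

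The formula agrees: 0.195 × 0.64 × 5 = 0.62 against 0.63, and 0.350 × 0.64 × 5 = 1.12. Unpaired loss by level is 0.39/5 = 0.08 to 0.70/5 = 0.14 SD. With SDs 4 and 2 (ρ = 16/20 = 0.8), the same-children bias for a steep fall drops to +0.17 and +0.31 points.

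**4. Only children able before the start.** SDs 3 and 4, ability meaning FVC above 30% predicted, mean starting FVC 60, 45 or 40; 7%, 17% or 21% then lose the ability by level. Unpaired bias is +0.26, +0.48 or +0.57 points. For the same children in both years it is −0.02, −0.07 or −0.08. With every able child followed in full it is −0.12, −0.41 or −0.53, because requiring ability at the start trims the worst before-year slopes.

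**5. An opposing effect.** Children who first become able after the start add after-year slopes only. If they are younger and decline faster, as Section 1.1 suggests, an unpaired comparison moves against saline by their share of the after-year slopes times the difference in slope. Neither quantity is in the documents.

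**The case against.** A reader might infer that the subgroup means those able at recruitment, that progression removes the ability, and that saline will therefore look protective. The documents support none of these as a certainty.

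- **Timing.** The wording carries no date. In a chart review it could equally mean children with spirometry on record. A child who later lost the ability could then still supply usable slopes. This stands; the defect is that the plan leaves the choice open.
- **Loss of ability.** Section 1.1 describes weak muscles and falling vital capacity. It never says that spirometry becomes impossible. The step is plausible, but it is an inference.
- **Direction.** Section 1.1 concerns low lung function, and loss by level gives zero bias when the same children supply both years. This stands as a limit on the claim. It does not protect the plan, because independent tests do not require the same children, and loss by level then gives +0.39 to +0.70 points. Newly able children may offset some of this.
- **Size.** With an assumed 20 paired children and ρ = 0.5, the standard error of the mean change is √(2 × 0.5/20) = 0.22 SD, larger than the same-children bias of 0.10–0.18 SD at that ρ. That is fair for a pilot, but a systematic error towards the hypothesis does not shrink with more children.
- **Remedy.** A child with no after-year test has no after-year slope under any definition. Redefining the subgroup is therefore not enough; the paired comparison and the sensitivity analysis are also needed.

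**Conclusion.** The point holds conditionally. An outcome listed as primary has an analysis population whose entry rule is undated in Section 2 and absent in Section 3.1, and the unpaired tests in Section 6 would allow children to drop out of the after-year only. If ability is judged after the start, or if unpaired slopes are compared, the result can favour saline with no true effect.

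At an assumed 10–20% loss the bias is 0 to about 0.35 SD of the slope. Where in that range it falls depends on why ability is lost and whether the comparison is within child. The net direction is not certain, because newly able children could act against saline. The actual size cannot be known from the documents. Confidence is medium, and the change is worth making because it is cheap.

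**What to change.** - **Subgroup.** Define it before treatment: neuromuscular disease and at least two spirometry results in the 12 months before starting saline. Use the same definition in Sections 2 and 3.1, and reconcile whether the outcome is primary or secondary.
- **Comparison.** Replace the independent tests in Section 6 with a within-child comparison: a paired test, or a mixed slope model using all available tests.
- **Reporting.** Give the number of children without after-year spirometry, the reasons, and their before-year slopes.
- **Sensitivity analysis.** Add a rank-based analysis of within-child change that gives the lowest rank to children who could no longer perform the test. Pairing alone does not remove bias from a steep after-start fall.

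**Cost.** This changes protocol and SAP wording and needs dated spirometry from charts already under review. How often children were tested is not stated, so the two-test minimum should be checked against the charts first. Children who first became able after starting, or who have fewer than two earlier tests, leave the comparison. The result may be less precise or less favourable; step 4 of the working suggests a residual of −0.12 to −0.53 points per year against saline with complete follow-up. The fix does not deal with decline easing naturally as children grow older, which affects any before/after comparison and is a separate matter.

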## Secondary Endpoints:

- Score on the ease of airway clearance pictorial analogue scale from all participants.
- Participants' perception of treatment.

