# Hypertonic saline treatment questionnaire PARENTS/LEGAL GUARDIAN

Participant II	D:								Date:	/	/
1)Overall, d had has bee		eel th	at neb	ulised	hypert	onic sa	line yo	ur child	l / your	ng perso	n has
	ul useful n't know	,									
What have yo	u found	most (	useful a	bout it?	•						
What have yo	u found	most o	difficult,	/ trouble	esome a	bout it?					
2)Please sco airway Before startin				ink it l	nas bee	n to cle	ear spu	tum fro	om your	child's	
0	1	2	3	4	5	6	7	8	9	10	
	+	+	$\dashv$	+	$\dashv$	+	$\dashv$	+	+	$\dashv$	
Most Easy		 							· • •	► Most D	ifficult
After starting	Hyperto	nic Sal	ine								
0	1	2	3	4	5	6	7	8	9	10	
1	1	1	- 1	- 1	- 1	- 1	- 1	- 1	- 1	1	
	$\top$	$\top$								$\dashv$	
Most Fasy										Most D	ifficult

Participant ID:		Date:/
In the 12 months before starting did your child need? If you don't		
Oral		
IV		
In the 12 months after starting H your child need? If you don't rem	· · · · · · · · · · · · · · · · · · ·	urses of antibiotics did
Oral		
IV		
In the 12 months before starting take your child to see a doctor be don't remember, please leave it b	ecause s/he was unwell with a	
In the 12 months after starting take your child to be seen by a do If you don't remember, please lea	octor because s/he was unwell	

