# Hypertonic saline questionnaire

[figure not shown]
Ages 16 to 18 years

Participant ID:	Date:	_/	_/
1)Overall, do you feel that nebulised hypertonic saline has been			
Useful Not useful I don't know			
What have you found most useful about it?			

[figure not shown]
What have you found most difficult/ troublesome about it?

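### No visible perception question asks parents to compare hypertonic saline with previous management, so the last secondary objective is only partly addressed

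*Combined protocol and SAP*

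**What the plan says.** - **Objective (section 2, last secondary objective).** The plan will explore how parents "perceive the treatment with nebulised hypertonic saline compared to previous management". This names a population (parents) and a comparator (the management that saline followed).
- **Endpoint (section 3.1, secondary endpoints).** The matching endpoint is "Participants' perception of treatment". It states no comparator. Ease of airway clearance is a separate secondary endpoint.
- **Analysis (section 6, Statistical Analysis Plan).** The whole entry is "Univariate analysis on perception of treatment". Ease of airway clearance has its own line.
- **Questionnaires (Appendices 1 to 3).** Item 1 on the form for ages 16 to 18 reads "Overall, do you feel that nebulised hypertonic saline has been", with the options "Useful Not useful I don't know". Two open questions follow: "What have you found most useful about it" and "What have you found most difficult/ troublesome about it". The parent form has the same structure, though its text is broken in extraction. The form for ages 10 to 15 asks in simpler words what the child likes and does not like about the treatment.
- **Before/after material on the parent form.** Parents score ease of clearing sputum from 0 (easiest) to 10 (most difficult), before and after starting saline. They also recall antibiotic courses (oral and intravenous) and illness-related doctor visits in the 12 months before and the 12 months after starting.

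**The concern.** An objective phrased as a comparison needs either a question that asks for the comparison or two measurements that can be contrasted. The perception item has neither. The share of parents who tick the favourable option describes saline alone. A high share is compatible with parents thinking saline better than, equal to or worse than what came before.

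Timing does not supply the missing contrast. Eligible children have already been on saline for at least 12 months, the assessment section is marked as not applicable, and no earlier or repeated administration of the form is described. Any comparison therefore has to come from the wording of the questions.

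At stake is one exploratory objective. The report would either leave its comparative part unanswered or risk presenting a single-treatment rating as though it were a comparison.

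**Working it through.** No sample-size or precision formula bears on this point, and the plan gives no figure to reproduce. The check is to follow the objective through to the data, then count what the parent form collects.

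**Step 1. Is the comparator carried forward?**

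| Stage | Where | Comparator with previous management? |
|---|---|---|
| Objective | Section 2 | Yes |
| Endpoint | Section 3.1 | None named |
| Analysis | Section 6 | None named; no contrast or pairing stated |
| Perception questions | Appendices 1 to 3 | None visible |

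**Step 2. What does the parent form (Appendix 1) collect?**

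| Type of question | Count | Bearing on the objective |
|---|---|---|
| Closed perception question on saline alone | 1 (three options) | No contrast |
| Open perception question on saline alone | 2 | No prompt to compare |
| Perception question comparing with previous management | 0 | This is what the objective calls for |
| Before/after rating | 1 (ease of clearing sputum, 0 to 10) | Partial: one dimension |
| Before/after recall topic | 2 (antibiotic courses; doctor visits) | Event counts, not perceptions |

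The parent perception block thus has 1 + 2 = 3 questions, of which 0 are comparative. The two forms for young people have the same 1 + 2 structure, so across the three forms the count is 0 of 3 × 3 = 9.

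**Step 3. Can the before/after material stand in?**

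The ease score is a rating by parents at two recalled time points, so it gives a real, if retrospective, comparison with the period before saline. It has three limits for this purpose:

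1. It covers ease of clearance only, and leaves out burden, tolerability and overall usefulness.
2. Sections 2, 3.1 and 6 each assign it to a separate objective, endpoint and analysis line, and nothing links it to the perception objective.
3. No visible question records what the previous management was, so the before score refers to a period, not to a described treatment.

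The antibiotic and doctor-visit items share the before/after layout but count events. They show that the form can ask in pairs. The perception block does not.

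**The case against.** The case on the other side has real force on several points.

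- **A reader might infer that the tick-box is all there is on perception.** It is not. Two open questions follow it on every form, and free text is a normal way to explore perception, which is all the objective promises. A parent may volunteer a comparison there. However, both questions ask about saline alone, nothing prompts a comparison, and no analysis of free text is described.
- **A reader might infer that the objective cannot be answered at all.** The documents do not support that. The parents' before/after ease score is a perceived comparison on one dimension, and nothing prevents its use for an exploratory objective. What stands is that the plan does not say it will be used that way.
- **A reader might infer that the endpoint moves from parents to patients.** It does not. Sections 3 and 6 count parents and legal guardians among the participants, and section 4.2 includes them. The endpoint is broader than the objective but still covers parents.
- **The parent material may be incomplete.** Section 3 says that parents complete two questionnaires, while only one parent form is listed and reproduced. The other may be the hospitalisation item named in section 3.1, but that is an assumption. A comparative question on it cannot be fully excluded, although none is described anywhere. The broken extraction of the parent form matters less, because the form for ages 16 to 18 shows the same item legibly.
- **A new better/same/worse item would itself be a single retrospective rating.** This is true, and it should be reported as such. It would still ask the question that the objective poses.

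**Conclusion.** The point holds in a limited form. The objective is comparative, while the perception questions, endpoint and analysis that serve it are not. Followed as written, the perception analysis can describe how many respondents found saline useful and what they liked or found troublesome. It cannot say how parents perceive saline relative to previous management. The only before/after rating by parents covers ease of clearing sputum and is assigned elsewhere, so the objective is partly addressed.

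The size is a matter of count, not of precision: none of the three visible parent perception questions is comparative. The number of forms returned does not change this.

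The conclusion rests on two assumptions: that the unreproduced second parent questionnaire holds no comparative perception question, and that the garbled parent form matches the legible form for ages 16 to 18 on item 1. The importance is low, since this is the last-listed secondary objective of a pilot study, but the mismatch is specific and cheap to remove.

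**What to change.** **Preferred.** Add one item to the parent form asking whether, compared with how the child's airway clearance was managed before, saline has been better, the same, worse, or don't know. Add a short line recording what that management was. In section 6, report the parents' answers as proportions with exact 95% confidence intervals, keep don't know in the denominator, and state that this is a single retrospective rating.

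**If the form cannot change,** choose one of two edits:

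1. State that the parents' before/after ease score serves this objective and narrow the objective to ease of clearance. Specify a paired analysis: the within-parent difference (after minus before) with a 95% confidence interval. Lower scores mean easier clearance, so a negative difference is an improvement.
2. Delete the comparative clause from the objective, so that it promises only a description of how parents perceive saline.

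**Also** confirm what the second parent questionnaire in section 3 is, and append it or name it. If it already holds a comparative item, a cross-reference in sections 3.1 and 6 is enough.

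**Cost.** The preferred route needs one questionnaire item, its short record line and an amendment. The alternatives are wording changes only.
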